12.1 Trial Hypotheses

The Primary Hypothesis:

- 38% Silver Diamine Fluoride (SDF) will arrest cavitated caries lesions (ICDAS 5 or 6) in primary teeth, measured by a change in dentin hardness, without a change in ICDAS severity score, after a single application (measured at approximately 6 months post initial application). This occurs as a result of the halting of the caries disease process, which occurs very soon after application of SDF due to its strong antimicrobial and remineralizing properties.

The Secondary Hypotheses:

- 38% Silver Diamine Fluoride (SDF) will arrest a greater proportion of cavitated caries lesions (ICDAS 5 or 6) in primary teeth after two applications, approximately 6 months apart (measured at approximately 8 months after initial SDF application).
- Lesions arrested approximately 3 months after a single application will remain stable when re-assessed at approximately 6 months.
- 38% Silver Diamine Fluoride (SDF) will decrease the proportion of children in pain, number of pain episodes associated with treated teeth for children, and pain score associated with treated teeth. The hypothesis is that SDF will do this as it is an anti-hypersensitivity agent, extremely efficient at blocking dentinal tubules, and also because it can arrest cavitated lesions, and thus decrease pain.

The Tertiary Hypotheses:

- 38% Silver Diamine Fluoride (SDF) will increase Oral Health-Related Quality of Life (OHRQoL) as a result of decreasing pain and arresting caries lesions.
- 38% Silver Diamine Fluoride (SDF) will be an acceptable treatment by parents/guardians of young children.

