12.4.2 Missing data

As noted in [Section 5.5](#), any lesions removed from the trial due to the “early exit strategy” will be considered to be treatment failures – non-arrest of the lesion and presence of pain and/or infection requiring removal of the tooth from the study – and not considered to be missing data.

The primary method for handling missing data will be to use a multiple imputation analysis, with imputations based on race/ethnicity, gender, age, trial site, initial ICDAS score, tooth location, treatment, and most recent prior visit results will be performed. Twenty-five imputed datasets will be created, and results will be combined using standard methods.

A sensitivity / tipping point analysis will also be performed to evaluate the MAR (missing at random) assumption for the missing primary efficacy outcome (caries arrest at approximately 6 months). A pattern-mixture approach to the missing data imputation (missing not at random, MNAR) will be applied to the logistic regression model used for imputing the missing caries arrest at approximately 6 months outcome from the variables described above. To represent MNAR, a range of shift parameters will be used to adjust the log odds ratios for the SDF-treated group. The tipping point will be identified as the amount of shift needed to change the statistical significance of the treatment comparison using the primary efficacy analysis. The size of the shift required to change the statistical significance will be used to gauge the plausibility of the MAR assumption.

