3.2. Secondary Outcome Measures

The following secondary outcomes associated with application of 38% SDF will be assessed (*key secondary endpoints to be tested in a secondary endpoint hierarchical strategy as described in Section 6.11.4 are italicized*):

- *Efficacy of 38% SDF to arrest Cavitated Caries Lesions when applied twice, approximately 6 months apart: lesion arrest will be measured at approximately 8 months post initial treatment to assess efficacy (Aim 2).* Compare (Sub-Aim 2a) the effect of one application of SDF measured at approximately 3 and 6 months post initial treatment.
- *Child's Pain (Aim 3): The pain outcome will be defined as the proportion of children in each treatment arm experiencing toothache pain.* Additional pain outcomes will be the number of episodes of pain associated with treated teeth for each child in each arm during the follow-up period and the average recorded pain score for children in each treatment arm. The presence of pain associated with a trial tooth will be defined as a score of 1 or higher using the Dental Discomfort Questionnaire (DDQ; See Protocol Appendix B and Section 8), which a trial examiner can associate with a trial tooth during a clinical visit. The number of pain episodes is the total of all in-person visits at which a DDQ score of 1 or higher is confirmed by the trial examiner to be associated with a trial tooth. The pain score will be calculated using the DDQ.

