The primary method for handling missing data for 6-month and 8-month efficacy analysis will be to use a multiple imputation analysis. Missing data follow a non-monotone missing pattern. The imputation will use fully conditional specification (FCS) methods. Imputations for lesion arrest and lesion pain will be based on race/ethnicity, gender, age, trial site, initial ICDAS score, tooth location, and lesion arrest results from prior visits using a logistic regression model. Imputations for the subject-level pain score and family outcomes will be based on race/ethnicity, gender, age, trial site, maximum initial ICDAS score for the subject, a non-arrested/arrested indicator for the subject (non-arrested if any of the subject’s study lesions are not arrested) at the ‘current’ visit or at the most recent prior visit if the ‘current’ visit is missing, and results at prior visits for the

outcome using a predictive mean matching model. Missing at random (MAR) will be assumed. Twenty-five imputed datasets will be created, and results from the analyses performed on each imputed dataset will be combined using standard methods via Proc MIAnalyze.

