6.11.4. Secondary Efficacy Hypotheses, Endpoints, and Analyses

The gatekeeping procedure will assess the hypotheses associated with the two key secondary endpoints in the following prescribed hierarchy. Each endpoint will be assessed using a two-sided $\alpha=0.1\%$ significance level, however the second endpoint in the hierarchy below will be gated by the first endpoint meeting significance. Otherwise, no inference will be drawn on the second endpoint in the hierarchy below, however results with p-values will still be calculated and presented in the table outputs.

1. Secondary Endpoint #1: Cavitated Caries Lesion Arrest at 8 months (Aim 2)

This secondary endpoint will be tested first. The same GEE model for binary outcomes as used for Aim 1 will be used to compare the proportion of arrested lesions at 8-months to examine Aim 2.

2. Secondary Endpoint #2: Pain (Aim 3)

This secondary endpoint will be tested second only if the first secondary endpoint reaches statistical significance.

Aim 3: At the 8-month visits, the proportion of treated lesions that have experienced pain during the follow-up period before or at the visit will be compared between the SDF and placebo-treated groups using GEE models with a logit link for the lesion-specific binary outcomes yes/no lesion pain at each visit, using an exchangeable correlation to account for non- independence among multiple treated lesions within a participant. The GEE models will include study site as a covariate due to stratified randomization by site.

Other Sub-Aim Secondary Endpoint Analyses:

For Sub-Aim 2a (Cavitated caries lesion arrest at 3 months), the same GEE model for binary outcomes as used for Aim 1 will be used to compare the proportion of arrested lesions at 3 months to examine Aim 2a. Sub-Aim 2a is not included in the hierarchical testing strategy.

For Sub-Aim 2b (Stability of the effect of one application of 38% SDF on caries lesion arrest between 3 and 6 months), a longitudinal (repeated measures) model for binary data that incorporates both the correlation within each subject at each time and across the time points will be used to compare the proportion of arrested caries lesions at 3 and 6 months. Study site will be included as a covariate due to stratified randomization by site.

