For Sub-Aim 3a (Pain at 3 and 6 months): At the 3-, 6-month visits, the proportion of treated lesions that have experienced pain during the follow-up period before or at the visit will be compared between the SDF and placebo-treated groups using GEE models with a logit link for the lesion-specific binary outcomes yes/no lesion pain at each visit, using an exchangeable correlation to account for non- independence among multiple treated lesions within a participant. The GEE models will include study site as a covariate due to stratified randomization by site.

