6.11.5. Tertiary Efficacy Hypotheses, Endpoints, and Analyses

The P-CPQ (Sub-Aim 4a), FIS (Sub-Aim 4a), and satisfaction and acceptability scores (Sub-Aim 4b) will be compared between the SDF and placebo-treated groups using analysis of covariance (ANCOVA). The models will include study site as a covariate due to stratified randomization by site. Additional ANCOVA models will consider the effects of covariates and their interactions with the treatment effect.

Changes in the color of treated lesions over time will be summarized by group.

The family's experiences with ECC, child's brushing and dietary habits, and color change will be examined as additional covariates for the analyses of satisfaction and acceptability scores.

The total number of episodes of pain associated with trial teeth per participant (calculated by adding all reports of pain throughout the trial verified by a clinical exam to be associated with a trial tooth) during the follow-up period and the DDQ scores will be summarized for the SDF and placebo treated groups. Due to the small number of participants with any pain, no statistical comparisons will be performed for the number of episodes of pain or the DDQ scores.

Additional analyses of the proportion of arrested lesions at 3-months, 6-months, and 8-months will extend the GEE models for binary outcomes to include covariates and their interactions with the treatment effect; covariates will include race/ethnicity, gender, age, trial site, initial ICDAS score, tooth location (anterior/posterior; as there are some data in the literature to suggest a difference in SDF efficacy) and number of affected teeth. Interactions of the covariates with treatment will be explored to examine the results for differential treatment effects. However, the analyses are not specifically powered to detect these interactions. Due to the small number of participants with any pain, no analyses which include covariate effects on the binary pain outcomes will be performed.

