9. CHANGES TO PLANNED PROTOCOL ANALYSES

Changes in SAP v3 from the protocol specified analyses include:

- The per protocol population definition was updated.
- Safety population was added.
- A testing strategy for key secondary endpoints was added.
- Safety analyses will be presented descriptively. Formal statistical testing for safety (adverse events) was removed.
- ITT2 and PP2 analysis populations were added (FDA request from pre-NDA meeting)
- Subgroup analyses for efficacy and safety was added (FDA request from pre-NDA meeting)

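### The second key secondary endpoint is defined as children in pain but tested as lesions with pain; the change is not listed, and no child-level test is left

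*SAP*

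**What the plan says.** SAP 3.2 italicises the endpoints that enter the key secondary hierarchy. The italicised pain endpoint is: "The pain outcome will be defined as the proportion of children in each treatment arm experiencing toothache pain". Protocol 3.2.2 gives the same definition. The hypothesis in Protocol 12.1 is that SDF "will decrease the proportion of children in pain". Protocol 12.4 plans to compare the proportion of participants with pain at 3, 6 and 8 months by CMH tests stratified by site.

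SAP 6.11.4 carries out the hierarchy. For Secondary Endpoint #2 at 8 months, "the proportion of treated lesions that have experienced pain during the follow-up period before or at the visit will be compared", by a GEE with logit link, exchangeable correlation within child and site as a covariate. Sub-Aim 3a follows the same pattern: "At the 3-, 6-month visits, the proportion of treated lesions that have experienced pain during the follow-up period before or at the visit".

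For the other two pain outcomes, SAP 6.11.5 states that "no statistical comparisons will be performed for the number of episodes of pain or the DDQ scores", because few participants had any pain. SAP section 9 lists six changes from the protocol. The closest one reads "A testing strategy for key secondary endpoints was added".

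**The concern.** Within the SAP, the endpoint named for the second gated step and the analysis assigned to it use different units. A lesion-level odds ratio does not estimate the proportion of children in pain. It combines how many children have pain with how many of their lesions are recorded as painful. A treatment that changed only the second component could pass the test, and one that spared children pain could fail it.

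The lesion count is also less firmly measured. The Dental Discomfort Questionnaire (DDQ) is answered once per child and the examiner links the pain to a trial tooth. The SAP does not say how pain in a tooth is assigned when that tooth carries several treated lesions.

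At stake is the trial's stated conclusion on children's pain. The primary endpoint and the first key secondary endpoint are not affected.

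**Working it through.** **Text check**

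| Place | Unit | Comparison |
|---|---|---|
| Protocol 3.2.2, 12.1 | child | definition and hypothesis |
| Protocol 12.4 (Aim 3, Sub-Aim 3a) | child | CMH by site at 3, 6 and 8 months |
| SAP 3.2 (italicised) | child | definition |
| SAP 6.11.4 (Endpoint #2, Sub-Aim 3a) | lesion | logit GEE |
| SAP 6.11.5 (episodes, DDQ score) | child | summaries only |
| SAP section 9 | not mentioned | not mentioned |

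SAP 6.11 does plan imputation of a subject-level pain score, but 6.11.5 rules out a comparison of DDQ scores, so this is not a remaining test.

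**Inputs from the documents.** 1144 children allocated 1:1, so 572 per arm; 10% attrition, so 0.9 × 572 ≈ 515; 3 lesions per child; two-sided 0.1% level, |z| > 3.29.

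**The plan's own figure.** There is no sample size or power for pain. The primary calculation reproduces. For 55% versus 45% at 80% power, n = (3.2905√0.5 + 0.8416√0.495)² / 0.10² = 852 lesions per arm. With design effect 1 + 2 × 0.5 = 2, this is 852 × 2 / 3 = 568 children per arm, 1136 in total against 1144 stated.

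**Assumed inputs.** The documents give no pain rate for design and no distribution of painful lesions. The only related figure, 8-12% in Protocol Appendix B, is for emergency visits among children waiting for operating-room treatment and is only a proxy.

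**Formula.** If a share p of children are in pain with k of 3 lesions each, the per-child lesion proportion has mean pk/3 and variance p(k/3)² − (pk/3)². The risk-difference z is the difference in means divided by √((v_placebo + v_SDF)/n).

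**(a) Same share of children in pain; k = 2 on placebo, 1 on SDF; p = 10%.**
- Placebo: mean 0.0667, variance 0.0444 − 0.0044 = 0.0400.
- SDF: mean 0.0333, variance 0.0111 − 0.0011 = 0.0100.
- z = 0.0333/√(0.0500/572) = 3.57. At p = 8% and 5%, z = 3.15 and 2.45. On the log-odds scale the three values are 3.90, 3.45 and 2.69.

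**(b) 10% versus 4% of children; k = 1 on placebo, 2 on SDF.**
- Lesions: variances 0.0100 and 0.0178 − 0.0007 = 0.0171; z = 0.0067/√(0.0271/572) = 0.97.
- Children: z = 0.06/√(2 × 0.07 × 0.93/572) = 3.98.

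**(c) 10% versus 4% of children; k = 1 in both arms.** Each child's lesion proportion is one third of the child's yes/no value, so the unpooled risk-difference z is the same for both units: 0.06/√((0.0900 + 0.0384)/572) = 4.00.

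**Simulated share of trials significant.** Rows (a) to (c): three equal sites, no missing data, site-adjusted logit model with child-clustered standard errors, CMH by site, 4000 trials each. Values at 515 per arm are in brackets. Rows (d) and (e): 572 per arm, with each painful child having one or two painful lesions at random (two in 50% or 20% of painful children, giving means of 1.5 and 1.2).

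| Case | Children in pain, placebo vs SDF | Painful lesions per painful child | Lesion rates | Lesion test | Child test |
|---|---|---|---|---|---|
| a | 10% vs 10% | 2 vs 1 | 6.7% vs 3.3% | 72% (65%) | 0.1% |
| a | 8% vs 8% | 2 vs 1 | 5.3% vs 2.7% | 56% (47%) | about 0.1% |
| a | 5% vs 5% | 2 vs 1 | 3.3% vs 1.7% | 28% (23%) | about 0.1% |
| b | 10% vs 4% | 1 vs 2 | 3.3% vs 2.7% | 0.3% (0.4%) | 78% (70%) |
| c | 10% vs 4% | 1 vs 1 | 3.3% vs 1.3% | 74% (66%) | 77% (70%) |
| d | 10% vs 10% | 1.5 vs 1.2 | 5.0% vs 4.0% | about 2% | about 0.1% |
| e | 10% vs 4% | 1.2 vs 1.5 | 4.0% vs 2.0% | 27% | 77% |

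A full exchangeable GEE on 400 trials of the first row gave 71%.

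**The case against.** The strongest reply is that the lesion unit looks deliberate. The imputation and analysis text in SAP 6.11 and 6.11.4 treats pain by lesion consistently, and the GEE handles clustering within a child, so it is a valid analysis of its own quantity. That is right: this is not a clustering error. It does not reconcile 6.11.4 with the definition in 3.2.

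Second, a fixed two-fold contrast in painful lesions is near a worst case, and SAP 6.11.5 says few participants had pain. Both points stand as limits on size. With equal child rates and the mild contrast in row (d), the lesion test passes in only about 2% of trials. Case (a) at 3% of children in pain gives 10%. At 5% versus 2% of children with one painful lesion each, both tests are weak: 22% for lesions and 30% for children. But the same mild contrast in the other direction, row (e), still costs the lesion test most of its power. The small number of children with pain is given as the reason for dropping other pain analyses, not for changing the unit.

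Third, section 9 introduces its list with the word include, so the list may not be exhaustive. Pain episodes and DDQ scores are still summarised by arm, and the protocol says secondary outcomes are not meant for labeling claims. All true. The omission is a reporting gap and not evidence of concealment, and descriptive information survives. What is lost is the formal test of the endpoint that the hierarchy names.

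**Conclusion.** The point holds on the text alone: a child-level definition, a lesion-level test, no entry in the change list, and no remaining test of the proportion of children in pain. Followed as written, the second gated step cannot support a conclusion about children.

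The numerical size is conditional. Every pain rate and every lesion count per painful child above is assumed. The two units nearly agree when painful lesions per painful child are similar in the arms, and they can reach opposite decisions in either direction when they are not. In case (a) the lesion difference is real, but it is not a difference in children. The change should be made, but it concerns a secondary conclusion and not the primary result.

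**What to change.** In SAP 6.11.4, define key secondary #2 and Sub-Aim 3a as any pain associated with a trial tooth by the visit, yes or no per child, compared with site stratification as in Protocol 12.4. Keep the lesion-level GEE as supportive.

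SAP 6.11 has no imputation rule for a child-level binary pain outcome, so one must be added: either derive it from the imputed lesion data or impute it directly. Include treatment among the predictors. Protocol 12.4.2 lists it ("initial ICDAS score, tooth location, treatment, and most recent prior visit results"), whereas the SAP list for lesion pain, which begins "Imputations for lesion arrest and lesion pain will be based on race/ethnicity, gender, age, trial site, initial ICDAS score", does not name it. State how results are pooled over the 25 imputations, for example a site-adjusted logistic model combined with Proc MIAnalyze, or a stated rule for pooling CMH statistics.

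If the lesion is the intended unit, redefine the endpoint in SAP 3.2, list and justify the change in section 9, state how tooth pain is assigned to lesions, and limit the conclusion to lesions.

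The cost is SAP wording, a short imputation and pooling specification, and one table. No new data are needed.

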Note: As this trial may enroll siblings, at the time of analyses we intend to explore the correlations within participants and correlations between siblings to aid in determining the appropriate modeling technique to use. As described above the current analysis plan uses GEE models to account for correlations among multiple cavities within a participant. The GEEs could be extended to account for siblings by correlating all cavities within a family, rather than within a participant. However, this assumes the same within family correlation. An alternative approach is to account for the two levels of correlations (cavities within participants, participants within families) by switching the analyses to use generalized linear mixed models (GLMM) instead of GEE. One difficulty we anticipate with a switch to GLMM is estimation of the random effects – the number of families with enrolled siblings may not be large enough to properly estimate the two random effects within the GLMMs.

Aim 2 (Cavitated caries lesion arrest at 8 months follow-up): The same GEE model for binary outcomes as used for Aim 1 will be used to compare the proportion of arrested lesions at approximately 8-months to examine Aim 2.

Sub-Aim 2a (Compare the effect of one application of 38% SDF at 3 and 6 months follow-up on caries lesion arrest): A longitudinal (repeated measures) model for binary data that incorporates both the correlation within each subject at each time and across the time points will be used to compare the proportion of arrested caries lesions at approximately 3 and 6 months. Trial site will be included as a covariate.

Aim 3 and Sub-Aim 3a (pain): At the 3-, 6-, and 8-month visits, the proportion of participants who have experienced pain with treated teeth during the follow-up period will be compared between the SDF and placebo-treated groups using Cochran-Mantel-Haenszel chi-square tests, with trial sites as the strata.

The total number of episodes of pain associated with trial teeth per participant (calculated by adding all reports of pain throughout the trial verified by a clinical exam to be associated with a trial tooth) during the follow-up period will be compared between the SDF and placebo treated groups using generalized linear models (GLMs) for count data, with trial site included as a covariate. The DDQ score will be compared between groups using analysis of covariance at each follow-up visit, with trial site included as a covariate.

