6.13. Subgroup Analyses for Efficacy & Safety

The primary efficacy endpoint and the two key secondary endpoints (using the ITT and ITT2 populations, as well as the adverse event summaries (using the Safety population) will be performed for the following subgroups:

- Gender (Male, Female)
- Ethnicity (Hispanic/Latino, Not Hispanic/Latino)
- Race (Black/African American, White, Asian, American Indian/Alaska Native, Multiracial, Not Reported)
- Age (Binary): < 2 years vs. ≥ 2 years of age
- Age (Chronological): 1, 2, 3, 4, 5 years of age

If any of the categories in the above variables have less than 5% of the analyses set, they may be combined with other (neighboring if ordinal) categories so that we have enough subjects in every category used in the subgroup analyses.

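### The key secondary pain test is in effect a pooled Wald test at 0.1% with no sparse-data or zero-cell method, although the SAP says few participants had pain

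*SAP*

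**What the plan says.** SAP 6.11.4 makes pain at 8 months the second key secondary endpoint, tested only if lesion arrest at 8 months is significant. On the level it says: "Each endpoint will be assessed using a two-sided $\alpha=0.1\%$ significance level". The pain comparison is made at lesion level "using GEE models with a logit link for the lesion-specific binary outcomes yes/no lesion pain at each visit", with exchangeable correlation within the child and site as a covariate.

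SAP 6.11 fills missing lesion pain by multiple imputation with 25 data sets, and "results from the analyses performed on each imputed dataset will be combined using standard methods via Proc MIAnalyze". No test statistic, standard-error type or rule for an arm without events is given.

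SAP 6.11.5 describes pain as sparse. For that reason it drops the comparisons of pain episodes and DDQ scores, and adds: "Due to the small number of participants with any pain, no analyses which include covariate effects on the binary pain outcomes will be performed". It gives no count. SAP 6.13 nevertheless asks for subgroup results by sex, ethnicity, race and age for "The primary efficacy endpoint and the two key secondary endpoints (using the ITT and ITT2 populations".

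Protocol 12.4 planned a child-level comparison of pain "using Cochran-Mantel-Haenszel chi-square tests, with trial sites as the strata", which is a score-type test. SAP 9 records that a key secondary testing strategy was added, but does not mention the change of pain test.

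**The concern.** MIAnalyze combines estimates and standard errors, so what is tested is a pooled log odds ratio divided by its standard error. When events are few, this Wald statistic behaves badly. The more extreme the split, the larger the standard error of the log odds, so strong evidence can produce a weak test. With no events in one arm, the log odds ratio has no finite value. A score or exact test does not have these defects.

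At 0.1% the effect is larger than at conventional levels. A clear difference in pain could be called non-significant because of the statistic chosen. With an empty arm, the answer could depend on a software option. Subgroup models meet the same problem with fewer events.

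**Working it through.** **Inputs.** Two-sided alpha is 0.001 (SAP 6.11.4), so the critical |z| is 3.2905. The sample is 1144 children at 1:1 (SAP 4 and 5), so 572 per arm. Lesions per child are 3 (SAP 4). The plan states no pain rate, event count or power for this endpoint, so pain rates below are assumptions.

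**The plan's own figure.** For 55% v 45%, 80% power and alpha 0.001, lesions per arm are (3.2905·√(2·0.5·0.5) + 0.8416·√(2·0.55·0.45))² / 0.10² = 852. The design effect is 1 + (3−1)·0.5 = 2. Then 852·2/3 = 568 children per arm, 1136 in total, against 1144 stated. This ignores attrition and the interim look. It supports using 0.001 and 572 per arm.

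**Child-level Wald test.** z = [ln(b/(572−b)) − ln(a/(572−a))] / √(1/a + 1/(572−a) + 1/b + 1/(572−b)), with a painful children on SDF and b on placebo.

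- 20 painful children: the best split is 2 v 18, with z = 2.98 and p = 0.0029. The same data give score p = 0.0003 and Fisher p = 0.0004.
- 24 (2 v 22): 2.434/0.741 = 3.284, p = 0.00102.
- 25 (2 v 23): 2.480/0.740 = 3.353, p = 0.0008. This is the first total that passes.
- Other splits need more: 1 v 28, 3 v 23 and 4 v 24.

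**Child-level score test.** z = (b/572 − a/572) / √(p(1−p)·2/572), with p = (a+b)/1144. At 0 v 11, 0.01923/0.00577 = 3.33 and Fisher p = 0.00093. At 0 v 10, z = 3.18, which does not pass.

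**Lesion level, as in the SAP.** Let k children in an arm each have q painful lesions out of 3, and let μ = kq/(572·3). The sandwich variance of the logit is [k(q−3μ)² + (572−k)(3μ)²] / [572·3·μ(1−μ)]².

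| Painful lesions per painful child (SDF, placebo) | Smallest total for significance |
|---|---|
| 1,1 or 2,2 or 3,3 | 25 (2 v 23) |
| 1,2 | 15 (2 v 13) |
| 1,3 | 11 (2 v 9) |

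A fitted exchangeable logistic GEE with site gives |z| = 3.34 at 2 v 23 and 3.27 at 2 v 22, so the 25 also holds for the fitted model.

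**Imputation.** In a simplified simulation (25 imputations, no covariates), the floor of 25 rises to about 28–32 with 5–10% missing. The unequal-lesion cases still pass at about 15–22 children.

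**No painful SDF child.** At 0 v 11, the model-based standard error gives z near 0, and the empirical sandwich gives a spurious |z| of about 81. Imputation can put events into the empty arm. The SAP's list ("Imputations for lesion arrest and lesion pain will be based on race/ethnicity, gender, age, trial site, initial ICDAS score, tooth location", then earlier arrest results) has no treatment term. With that list, one painful lesion per child and at least 5% missing, a zero split is almost never significant below 25 children. With treatment in the imputation model, the spurious result returns in 81–98% of runs at 5–10% missing. An empty arm is not remote: at a true SDF rate of 0.5%, its probability is 0.995^572 = 5.7%.

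**Power at 0.1%.** Exact binomial enumeration, 572 per arm, one event per child, unstratified, no imputation. An empty arm counts as not significant for Wald.

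| Pain, placebo v SDF | Expected painful children | Wald | Score |
|---|---|---|---|
| 3% v 0.5% | 20 | 6% | 50% |
| 4% v 1% | 29 | 27% | 50% |
| 5% v 1% | 34 | 65% | 80% |
| 6% v 2% | 46 | 50% | 58% |
| 12% v 6% | 103 | 59% | 61% |

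With 2% pain in both arms, the true size is about 0.00004 for Wald and 0.0008 for the score test, against a nominal 0.001. The score test's advantage is therefore not bought with excess type I error.

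**The case against.** **The floor of 25 is conditional.** A reader might infer that fewer than 25 painful children can never give significance, however they split. The lesion-level calculation does not support that: the floor falls to 15 or 11 if placebo children have more painful lesions each. This stands.

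**The failure is not only towards a missed benefit.** A reader might infer that an empty SDF arm simply yields no result. With an empirical standard error it yields false significance. This also stands, and it strengthens the case for naming the method.

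**The trial is not shown to be in the sparse range.** Twenty-five children are 2.2% of 1144. The only rate in the documents, in Protocol Appendix B, is 8–12% emergency visits for toothache during an operating-room wait. Applied here, that is 92–137 children, where the two tests nearly agree. It is outside experience, however, and SAP 6.11.5 points lower.

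**Wald is inferred.** The SAP does not use the word. The inference follows from pooling by MIAnalyze and should be presented as an inference.

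**Subgroups have a safeguard.** A reader might infer that pain odds ratios in subgroups are bound to be undefined. SAP 6.13 lets categories below 5% of the analysis set be merged, and results by sex may well be estimable. But 5% of 1144 is 57 children, and the rule looks at subjects, not at pain events. The restriction in 6.11.5 concerns covariate effects, so 6.13 is in tension with it rather than in contradiction.

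**The consequence is limited.** Nothing is tested after pain, p-values are shown regardless of the gate, and Protocol 3.1 and 3.2.2 say the pain aim is not meant for labeling claims.

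**Conclusion.** The concern holds in a limited form. The SAP puts a confirmatory test at 0.1% on an outcome that it calls sparse, by a method that is Wald-type in effect, and gives no rule for few or zero events.

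Given 572 children per arm, equal painful lesions per painful child and at least one painful child in each arm, about 25 painful children are needed, against 11 for a child-level score or Fisher test. With 430–515 children per arm the floor is 24–25, so attrition hardly changes it.

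The cost in power runs from 44 percentage points (3% v 0.5%) to 2 points (12% v 6%). The documents do not show where in that range the trial lies, so they do not support saying that a real benefit will be missed. They do support saying that the outcome of the test can depend on choices the SAP leaves open. This is a worthwhile, inexpensive improvement. It does not affect the primary endpoint.

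**What to change.** In SAP 6.11.4, base the pain decision at 0.1% on a site-stratified score or exact test. This can be the child-level Cochran-Mantel-Haenszel test of the protocol, in exact form if events are few, or a GEE score test if lesions remain the unit. State how that test is combined over imputations, or that it uses verified pain status only. Name the standard error for any GEE that is kept and say what is done when an arm has no pain. Report a Firth-type odds ratio and a risk difference as estimates.

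In SAP 6.13, report pain subgroups as counts and percentages by arm where events are few, and tie that rule to pain events rather than to subjects.

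The cost is rewording, a different procedure and extra work to pool the test, since score and exact tests do not pass through MIAnalyze as directly as an estimate and its standard error.
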